2 PROTOCOL SYNOPSIS

| | |
|---|--|
| Title | A Phase 3, Open-label Study Evaluating the Long-term Safety and Efficacy of VX-445 Combination Therapy in Subjects With Cystic Fibrosis Who Are Heterozygous for the F508del Mutation and a Gating or Residual Function Mutation (F/G and F/RF Genotypes) |
| Brief Title | A Study Evaluating the Long-term Safety and Efficacy of VX-445 Combination Therapy |
| Clinical Phase and Clinical Study Type | Phase 3, safety and efficacy |
| Objectives | 
Primary Objective
 
To evaluate the long-term safety and tolerability of VX-445/tezacaftor (TEZ)/ivacaftor (IVA) in subjects with cystic fibrosis (CF) who are heterozygous for the F508del mutation and a gating (F/G) or residual function (F/RF) mutation
 
Secondary Objectives
 
 • To evaluate the long-term efficacy of VX-445/TEZ/IVA • To evaluate the pharmacodynamics (PD) of VX-445/TEZ/IVA |
| Endpoints | 
Primary Endpoint
 
Safety and tolerability of long-term treatment with VX-445/TEZ/IVA based on adverse events (AEs), clinical laboratory values, ECGs, vital signs, and pulse oximetry
 
Secondary Endpoints
 
 • Absolute change in percent predicted forced expiratory volume in 1 second (ppFEV₁) • Absolute change in sweat chloride (SwCl) • Absolute change in body mass index (BMI) • Absolute change in BMI z-score • Absolute change in body weight • Absolute change in Cystic Fibrosis Questionnaire-Revised (CFQ-R) respiratory domain (RD) score 
Exploratory Endpoints
 
 • Absolute change in CFQ-R non-RD scores • Inflammatory mediators • Blood biomarkers |
| Number of Subjects | Subjects who complete the last Treatment Period visit in the parent study (Study VX18-445-104 [Study 104]) and meet eligibility criteria are eligible to enroll. Approximately 250 subjects are expected to enroll. |
| Study Population | Male and female CF subjects 12 years of age or older with F/G or F/RF genotypes |

Investigational Drug Study drug refers to VX-445/TEZ/IVA and IVA

Study drugs will be orally administered as 2 fixed-dose combination (FDC) film-coated tablets of VX-445/TEZ/IVA in the morning, and 1 film-coated IVA tablet in the evening.

Active substance: VX-445/TEZ/IVA

Activity: VX-445 is a CFTR corrector, TEZ is a CFTR corrector, and IVA is a CFTR potentiator (increased Cl⁻ secretion)

Strength: 100 mg/50 mg/75 mg FDC tablet

Active substance: IVA

Activity: CFTR potentiator (increased Cl⁻ secretion)

[figure not shown]
Strength: 150 mg tablet

Study Duration The total study duration is approximately 100 weeks (from the first dose of study drug in this study), including a 96-week Treatment Period and a 4-week Safety Follow-up Period.

Study Design This is a Phase 3, multicenter, open-label study for subjects who completed the last Treatment Period visit in the parent study (Study 104) and meet eligibility criteria (Figure 2-1).

All subjects will receive the triple combination (TC) of VX-445/TEZ/IVA at the same dosage as that evaluated in Study 104.

Figure 2-1 VX18-445-110 Study Design

IVA: ivacaftor; TEZ: tezacaftor
 Note: Parent study refers to Study 104.

Assessments

Safety: AEs, clinical laboratory assessments, ECGs, vital signs, pulse oximetry, physical examinations, and ophthalmologic examinations (for subjects <18 years of age on the date of informed consent in the parent study)

Efficacy: Spirometry, height (for ≤21 years of age), weight, and CFQ-R

PD: SwCl

Exploratory: Inflammatory mediators, blood biomarker samples, and sputum samples

Statistical Analyses The primary objective of the study is the evaluation of the long-term safety and tolerability of VX-445/TEZ/IVA. The safety endpoints of long-term treatment include AEs, clinical laboratory values, ECGs, vital signs, and pulse oximetry from the first dose of study drug in the open-label study, for subjects who received at least 1 dose of study drug in the open-label study. The safety analysis will be descriptive only.

The secondary objective of the study is the evaluation of long-term efficacy and PD of VX-445/TEZ/IVA, as assessed by spirometry, SwCl, BMI, BMI z-score, weight, and CFQ-R. Methods of efficacy analyses will be similar as those used in the parent study.

Interim Analyses Interim analyses (IAs) may take place at any time during the study at the discretion of the sponsor. In the event that the parent study is still ongoing, a limited Vertex team may be unblinded to the treatment assignments in the parent study for the purpose of reviewing the interim results and will not be involved in or influence the conduct of the remaining part of the parent study to protect the integrity of the parent study.

IDMC Reviews The independent data monitoring committee (IDMC) will conduct periodic safety reviews of study data as outlined in the IDMC charter.

3 SCHEDULE OF ASSESSMENTS

The schedule of assessments is in [Table 3-1](#). All visits will be scheduled relative to the Day 1 Visit in this study.

The Cystic Fibrosis Questionnaire–Revised (CFQ-R) must be completed before any other assessment (except signing of the informed consent form [ICF]) at relevant clinic visits. Remaining assessments may be performed in any order when more than 1 assessment is required at a particular time point. All assessments will be performed before study drug dosing (Section [9.6.1](#)), unless noted otherwise.

Table 3-1 VX18-445-110: Treatment Period and Safety Follow-up Visit

| Event/Assessment ^a | Treatment Period | | | | | | | ETT Visit ^b | Safety Follow-up Visit 28 (± 7) Days After Last Dose ^c | Comments |
|---|--------------------|-------------------|-----------------------------------|---|--------------------|-----------------------------|--------------------|------------------------|---|---|
| | Day 1 ^d | Day 15 (± 3 Days) | Weeks 4, 8, 16, 24, 36 (± 5 Days) | Weeks 12, 20, 28, 32, 40, 44, 52, 56, 64, 68, 76, 80, 88, 92 (± 5 Days) | Week 48 (± 5 Days) | Weeks 60, 72, 84 (± 5 Days) | Week 96 (± 5 Days) | | | |
| Clinic visit | X | X | X | | X | X | X | X | X | |
| Telephone contact | | | | X | | | | | | Assess the subject's status, any AEs, concomitant medications, treatments, and procedures |
| ICF and assent (when applicable) | X | | | | | | | | | Section 8 |
| Inclusion and exclusion criteria confirmation | X | | | | | | | | | Section 8 |
| CFQ-R | X | | Weeks 4, 8, 24 | | X | Week 72 | X | X | X | Must be completed before any other assessments (except signing of ICF) at relevant clinic visits (Section 11.5.3) |
| Weight and height | X | X | X | | X | X | X | X | X | Measured with shoes off. Height will be collected only for subjects ≤21 years of age (Section 11.5.2) |

^a All assessments will be performed before study drug dosing (Section 9.6.1), unless noted otherwise.

^b If the subject prematurely discontinues study drug treatment, an ETT Visit should be scheduled as soon as possible after the decision to discontinue treatment (Section 9.1.3).

^c The Safety Follow-up Visit is required for all subjects. Refer to Section 9.1.2 for subjects who transition to a commercially available or managed access program-supplied next-generation corrector TC regimen. For subjects who complete an ETT Visit 3 weeks or later following the last dose of study drug, the ETT Visit will replace the Safety Follow-up Visit (Section 9.1.3).

^d The Day 1 Visit of this study should be on the same day as the last scheduled visit of the parent study. Subjects whose Day 1 Visit is NOT within 1 day of the last scheduled visit in the Treatment Period of the parent study will have all Day 1 assessments performed (Section 9.1.1). Subjects whose Day 1 Visit is within 1 day of the last scheduled visit in the Treatment Period of the parent study will NOT have to repeat assessments that were performed as part of the last scheduled visit of the parent study Treatment Period.

Table 3-1 VX18-445-110: Treatment Period and Safety Follow-up Visit

| Event/Assessment ^a | Treatment Period | | | | | | | ETT Visit ^b | Safety Follow-up Visit 28 (± 7) Days After Last Dose ^c | Comments |
|--------------------------------------|--------------------|-------------------|-----------------------------------|---|--------------------|-----------------------------|--------------------|------------------------|---|---|
| | Day 1 ^d | Day 15 (± 3 Days) | Weeks 4, 8, 16, 24, 36 (± 5 Days) | Weeks 12, 20, 28, 32, 40, 44, 52, 56, 64, 68, 76, 80, 88, 92 (± 5 Days) | Week 48 (± 5 Days) | Weeks 60, 72, 84 (± 5 Days) | Week 96 (± 5 Days) | | | |
| OE | | | | | X | | X | X | | Subjects <18 years of age on the date of informed consent in the parent study will have an OE within 28 days of the Week 48 and Week 96 Visits. In addition, an OE will be performed within 28 days of the ETT Visit for subjects whose cumulative study drug exposure (in the parent study and current study) is at least 12 weeks since their last study OE. (Section 11.6.6) |
| Complete physical examination | X | | | | | | X | X | | Section 11.6.3 |
| Pregnancy test (all female subjects) | Urine | | Urine | Urine | Urine | Urine | Serum | Serum | Serum | At telephone contact visits, a urine pregnancy test will be performed with a home kit provided by the study site (Section 11.6.2) |
| Serum FSH | | | | | | | | | | As needed for any suspected postmenopausal female with at least 12 months of continuous spontaneous amenorrhea (Section 11.6.2) |

Table 3-1 VX18-445-110: Treatment Period and Safety Follow-up Visit

| Event/Assessment ^a | Treatment Period | | | | | | | ETT Visit ^b | Safety Follow-up Visit 28 (± 7) Days After Last Dose ^c | Comments |
|-------------------------------|--------------------|-------------------|-----------------------------------|---|--------------------|-----------------------------|--------------------|------------------------|---|---|
| | Day 1 ^d | Day 15 (± 3 Days) | Weeks 4, 8, 16, 24, 36 (± 5 Days) | Weeks 12, 20, 28, 32, 40, 44, 52, 56, 64, 68, 76, 80, 88, 92 (± 5 Days) | Week 48 (± 5 Days) | Weeks 60, 72, 84 (± 5 Days) | Week 96 (± 5 Days) | | | |
| Standard 12-lead ECG | X | X | Weeks 4, 8, 24 | | X | Week 72 | X | X | X | After subjects have rested for at least 5 minutes and before dosing, as applicable (Sections 11.6.3, 11.6.4, and 11.6.5) |
| Vital signs | X | X | X | | X | X | X | X | X | |
| Pulse oximetry | X | X | X | | X | X | X | X | X | |
| Spirometry | X | X | X | | X | X | X | X | X | Before dosing, as applicable, and should be performed pre-bronchodilator (Section 11.5.1) |
| SwCl | X | X | Weeks 4, 8, 24 | | X | Week 72 | X | X | | Must occur before dosing. At each time point, 2 samples will be collected, 1 from each arm (left and right) (Section 11.3). |
| Urinalysis | X | | | | Week 48 | | X | X | | Section 11.6.2 |
| Hematology | X | X | X | | X | X | X | X | X | Section 11.6.2 |
| Coagulation | X | | Weeks 4, 24 | | X | Week 72 | X | X | X | Section 11.6.2 |
| Serum chemistry | X | X | X | | X | X | X | X | X | Section 11.6.2 |
| Inflammatory mediator samples | X | | Weeks 4, 24 | | | | X | X | | Section 11.4.1 |
| Blood biomarker samples | X | | Weeks 4, 24 | | | | X | X | | Section 11.4.2 |
| Blood sample for RNA | X | | Weeks 4, 24 | | | | X | X | | Section 11.4.2 |
| Sputum samples | X | | Weeks 4, 24 | | | | X | X | | Collected from subjects who can produce a sample spontaneously (Section 11.4.3) |
| Study drug count | X | X | X | | X | X | X | X | | Section 10.6 |

Table 3-1 VX18-445-110: Treatment Period and Safety Follow-up Visit

| Event/Assessment ^a | Treatment Period | | | | | | | ETT Visit ^b | Safety Follow-up Visit 28 (± 7) Days After Last Dose ^c | Comments |
|----------------------------------|--|-------------------|-----------------------------------|---|--------------------|-----------------------------|--------------------|------------------------|---|---|
| | Day 1 ^d | Day 15 (± 3 Days) | Weeks 4, 8, 16, 24, 36 (± 5 Days) | Weeks 12, 20, 28, 32, 40, 44, 52, 56, 64, 68, 76, 80, 88, 92 (± 5 Days) | Week 48 (± 5 Days) | Weeks 60, 72, 84 (± 5 Days) | Week 96 (± 5 Days) | | | |
| Study drug dosing | Day 1 through evening before Week 96 Visit | | | | | | | | | Section 9.6.1 |
| Medications review | Continuous from signing of the ICF through completion of study participation | | | | | | | | | Completion of study participation is defined in Section 9.1.5 |
| Treatments and procedures review | | | | | | | | | | |
| AEs and SAEs | Continuous from signing of the ICF through completion of study participation | | | | | | | | | Sections 13.1.1.3 and 13.1.2.2 |

AE: adverse event; CFQ-R: Cystic Fibrosis Questionnaire-Revised; ETT: Early Termination of Treatment; FSH: follicle-stimulating hormone; ICF: informed consent form; OE: ophthalmologic examination; SAE: serious adverse event; SwCl: sweat chloride; TC: triple combination

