9.1.3 Early Termination of Treatment

If a subject prematurely discontinues study drug treatment, an ETT Visit should be scheduled as soon as possible after the decision to discontinue treatment.

If the ETT Visit occurs 3 weeks or later following the last dose of study drug, then the ETT Visit will replace the Safety Follow-up Visit, and a separate Safety Follow-up Visit will not be required.

During the course of study conduct, if local health authorities decline to approve the TC of VX-445/TEZ/IVA, or if clinical benefit is not demonstrated for the use of the TC for the treatment of CF in specific subpopulations enrolled in this study, subjects with the relevant *CFTR* genotypes may be discontinued after communication to investigators and IRBs/IECs of the risks/benefits related to the safety and efficacy observed for the relevant subset of subjects.

If a subject withdraws from the study and also withdraws consent or assent, no further assessments will be performed. Vertex may retain and continue to use any data and samples collected before such withdrawal of consent or assent.

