8.2 Open Label Extension Period

OL Efficacy Period for Part A: The time from the first dose of study drug in the OLS to the last efficacy assessment, which may be collected up to the Week 96 Visit or the earlier of Day 673 and the end of study participation if subject does not have the Week 96 Visit. This analysis period will be used with the OL-FAS for Part A to analyze the efficacy data during the OLS.

OL Safety Period for Part A: The time from the first dose of study drug in the OLS to 28 days after the last dose date of the study drug in the OLS or to the completion date of study participation (defined in CSP Section 9.1.5) in Part A, whichever occurs first. This analysis period will be used with the OL-SS for Part A to analyze the safety data during the OLS.

The **Treatment-emergent (TE) Period for Part A** is same as the OL Safety Period for Part A.

Note: for subjects who depart study 110 to participate in another qualified Vertex study and return in study 110, the above defined analysis period will exclude the time between the last dose before the discontinuation from study 110 and the first dose after re-enter in study 110.

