
Notes:
 
¹ Visit name for analysis purpose is used to report data in tables and figures.
 
² The analysis visit windows will be applied using the following rules for both scheduled and unscheduled visits:
 
 1. If no numerical measurement is available within a visit window, the measurement will be considered missing for the visit. 2. If there is more than 1 numerical measurement available within a visit window, use the following rules: 
 i. The measurement closest to the target day will be used; or ii. If there are multiple measurements with the same closest distance from the target day, the latest measurement will be used. For multiple measurements on the same day, unscheduled measurements will be treated as later than scheduled measurement. 
³ For measurement collected on the date of first dose of study drug in Treatment Period, if it cannot be determined whether the measurement is before or after the first dose:
 
 a. Scheduled measurement will be treated as pre-dose observation. b. Unscheduled measurement will be treated as post-dose observation. 			

Table 12-1 Analysis Visit Windows for Safety and Efficacy Assessments			
Assessment	Visit¹	Target Study Day	Analysis Visit Window (in study days)^{2, 3,4,5}

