
⁴ For safety Assessment, Safety Follow-up analysis visit will be based on nominal Safety Follow-up visit. If a subject doesn't have a nominal Safety Follow-up visit but has an ETT visit with study day >687, then the ETT visit will be mapped into Safety Follow-up analysis visit.
 
⁵ For efficacy assessment, if a subject has nominal safety follow up visit with study day >687, then nominal Safety Follow-up visit will be mapped to Safety Follow-up visit; else if subject doesn't have a nominal safety follow-up visit with study day > 687 but has an ETT visit with study day >687, then the ETT visit will be mapped into Safety Follow-up analysis visit; else if there are multiple assessments with >687 then select the earliest record.
 
⁶Weight will also be used in the threshold analysis in which the TC safety baseline will be used to calculate change.
 
Derived Variables:
 
 Age (in years) at first dose date and post-baseline visit (for demographics, listing and the calculation of [percent] predicted spirometry variables): 
Obtain the age at informed consent in “yy, mm” format (e.g., 24 years, 6 months) in parent study from the Vital Signs (VS) page at the Screening Visit in parent study, and add 0.5 month to convert to days.
 
Obtain the informed consent date in parent study.
 
Then age (in years) at first dose or post-baseline visit = [(first dose date or post-baseline visit date – informed consent date in parent study) in days + age at informed consent (in days) in parent study]/365.25.
 Age (in months) at first dose date and post-baseline visit (for use in calculation of BMI and weight z-score): 
Obtain the age at informed consent in “yy, mm” format (e.g., 24 years, 6 months) in parent study from the VS page at the Screening Visit in the parent study.
 
Obtain the informed consent date in parent study.
 
Then age (in months) at first dose or post-baseline visit = integer part of {[age at informed consent (in months) in parent study + 0.5 + diff(first dose date or post-baseline visit date, informed consent date) in months in parent study]} + 0.5.
 Missing first dose date or last dose date 
If the first dose date is missing, use Day 1 visit date.
 
If the last dose date of study drug is not available and there is no data to indicate that the subject discontinued treatment, the data cutoff date will be used instead.
 
If the subject discontinued treatment and the last dose date is missing or partial date is reported, the last dose date will be imputed based on, in descending order priority, the Early Treatment Termination (ETT) visit date, last visit date before the Safety Follow-up, or the last study drug administration date from EX SDTM domain, as appropriate. The imputation algorithm will ensure the imputed last dose date does not exceed the study participation end date.
 Electrocardiogram: 
Baseline is defined in Section 8.1. If multiple ECG measurements are obtained on the same calendar day during the TE period for Part A,
 
 ○ For summary purpose, the average value will be used as the ECG on that day; ○ For threshold analysis purpose, all ECG values will be used 			

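### SAP Table 12-1 note 4 tests study day instead of days off drug, so most ETT Visits that replace the Safety Follow-up Visit are assigned to treatment-visit safety windows

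*Protocol*

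**What the plan says.** **Protocol.** Table 3-1 footnote c reads, in part, "subjects who complete an ETT Visit 3 weeks or later following the last dose of study drug, the ETT Visit will replace the Safety Follow-up". Section 9.1.2 repeats the rule. Section 9.1.3 opens it with "If the ETT Visit occurs 3 weeks or later following the last dose of study drug" and adds that no separate Safety Follow-up Visit is then needed. Section 9.1.5 makes the replacing visit the completion of study participation. The trigger is time since the last dose; study day plays no part.

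**SAP Section 12.1, safety data.** In Table 12-1 the Safety Follow-up row for safety assessments is filled by nominal visit, on any study day. Note 4 provides for subjects without one: "If a subject doesn't have a nominal Safety Follow-up visit but has an ETT visit with study day >687", in which case that visit goes to the Safety Follow-up row. Otherwise the day windows decide: "The analysis visit windows will be applied using the following rules for both scheduled and unscheduled visits". When a window holds several measurements, "The measurement closest to the target day will be used".

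**SAP Section 12.1, efficacy data.** Note 5 applies the Day 687 test to both kinds of visit. The nominal visit is covered by "if a subject has nominal safety follow up visit with study day >687, then nominal Safety Follow-up visit will be mapped to Safety Follow-up visit", and the ETT Visit by a similar clause.

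**SAP Section 8.2.** The OL Safety Period, which is also the TE Period, runs from the first open-label dose "to 28 days after the last dose date of the study drug in the OLS or to the completion date" of study participation, whichever is first. Section 9.4 bases all safety analyses on it.

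**The concern.** Note 4 handles a subject who has an ETT Visit and no nominal Safety Follow-up Visit. The protocol's replacement rule produces exactly that subject. But ETT Visits belong to subjects who stop early, and Day 687 lies after the planned end of treatment. The clause can therefore work only for subjects who stop shortly before Week 96.

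The result is that like subjects are labelled unlike. Take two subjects whose last dose was on Day 150 and who are both seen on Day 175, 25 days off drug. If the visit is a nominal Safety Follow-up Visit, the chemistry value goes to the Safety Follow-up row. If it is a replacing ETT Visit, it falls in the window (141, 211] and becomes 'OL Week 24'.

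At stake are the by-visit summaries of laboratory values, ECGs and vital signs, which belong to the primary endpoint. Some 'OL Week x' rows would hold values from subjects three to four weeks off drug, and the Safety Follow-up row would lack them.

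**Working it through.** **Inputs from the documents**
- Replacement rule: 21 days or more after the last dose (protocol Table 3-1 footnote c, Section 9.1.3).
- Week 96 target Day 673; last treatment window (631, 687] (SAP Table 12-1).
- Planned dosing through the evening before the Week 96 Visit (protocol Table 3-1), so the planned last dose is about Day 672 and a premature stop has its last dose on about Days 1 to 671.
- TE Period ends at most 28 days after the last dose (SAP Section 8.2).

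**Assumptions, not in the documents**
- ETT delay of 21, 28 or 35 days.
- Last-dose days spread evenly over Days 1 to 671 or, as a contrasting case, over Days 589 to 671 (the last 12 weeks).

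**1. The plan's own figure.** Week 96 is 7 × 96 + 1 = Day 673. Adding 28 days gives Day 701. The midpoint is (673 + 701)/2 = Day 687. The cut therefore fits a subject who completes 96 weeks of treatment.

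**2. Last dose needed to pass note 4.** An ETT Visit *k* days after last-dose day *L* falls after Day 687 only if *L* ≥ 688 − *k*.

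| Days off drug, *k* | Earliest *L* that passes | Share at Day 687 or earlier, stops over Days 1-671 | Share at Day 687 or earlier, stops over Days 589-671 |
|---|---|---|---|
| 21 | 667 | 666/671 = 99.3% | 78/83 = 94.0% |
| 28 | 660 | 659/671 = 98.2% | 71/83 = 85.5% |
| 35 | 653 | 652/671 = 97.2% | 64/83 = 77.1% |

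These are shares of replacing ETT Visits assigned to a treatment-visit window.

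**3. The TE limit.** Up to 28 days off drug, the value lies in the TE Period and can enter a by-visit safety table. Beyond 28 days it is outside the TE Period and appears in no safety visit row. For safety data, only the 21-to-28-day band matters.

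**4. The closest-to-target rule.** Assume that on-drug visits took place on their target days. If a window's target day is on or before *L*, the on-drug value is closer and displaces the ETT value. Passing each *L* from 1 to 671 through the windows gives:

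| Safety windows | *k* | ETT value used as 'OL Week x' | Displaced by an on-drug visit | After Day 687 |
|---|---|---|---|---|
| Chemistry, hematology, vital signs | 21 | 77.2% | 22.1% | 0.7% |
| Chemistry, hematology, vital signs | 28 | 84.5% | 13.7% | 1.8% |
| ECG | 21 | 65.3% | 34.0% | 0.7% |
| ECG | 28 | 68.4% | 29.8% | 1.8% |

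Coagulation has its own windows and was not enumerated.

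**5. How many subjects.** The documents give neither a discontinuation rate nor ETT delays. As an illustration only, if 10% to 20% of about 250 subjects stop early and 10% to 20% of those have a late ETT Visit, the count is 250 × 0.10 × 0.10 = 2.5 to 250 × 0.20 × 0.20 = 10. That is before removing values past 28 days and displaced values.

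**The case against.** The case on the other side is substantial, and much of it stands.

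- **The protocol rule is operational.** It says when a separate visit is unnecessary and does not prescribe analysis windows, so this is not a direct contradiction. That is fair. But note 4 exists to carry such ETT Visits to the Safety Follow-up row, and its test defeats that purpose for almost all early stoppers.
- **Days 21 to 28 off drug are treatment-emergent by definition.** Protocol and SAP agree on this, so including those values in safety tables is by design. This stands. The fault is the visit label.
- **A reader might infer that nearly all replacing ETT Visits are reported as on-treatment values.** The documents do not support that. Values past 28 days leave the TE Period, and the closest-to-target rule displaces others, about a third of ECG values at 21 days. The 97-99% describes assignment to a window, not use in a table, and depends on an even spread of stopping.
- **A reader might infer that recovered values pull visit means toward normal.** No reasons for discontinuation are given, and protocol Section 9.9 allows many that are unrelated to safety findings. The direction is not established.
- **Much of the safety analysis does not use the visit label.** Threshold analyses (SAP Sections 9.4.2 to 9.4.4), maximum and minimum values (Section 9.1) and AE tables draw on the whole TE Period. This stands.
- **Late ETT Visits should be rare.** Protocol Section 9.1.3 asks for the visit as soon as possible. This stands.

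**Conclusion.** The inconsistency is real and minor. Note 4 files a nominal Safety Follow-up Visit by name on any day, but holds a replacing ETT Visit to a study-day test that can be met only with a last dose in about the last three weeks of a 96-week period. Most replacing ETT Visits are assigned to a treatment-visit window: about 97-99% with evenly spread stopping, about 77-94% if all stops fall in the last 12 weeks. Both spreads and the 21-to-35-day delay are assumptions.

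The effect on reported safety results is narrower. It concerns values 21 to 28 days off drug that are closest to the target day, in by-visit descriptive tables only. The number of subjects is unknown and probably small, so any shift in a visit mean should be small.

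For efficacy, a reader might infer the same unequal treatment. The documents do not support that: note 5 holds the nominal Safety Follow-up Visit and the ETT Visit to the same Day 687 test, so it treats both alike. The OL Efficacy Period sets no limit on days off drug. Whether off-drug values belong in the MMRM is a separate choice and is not decided here.

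**What to change.** In SAP Table 12-1 note 4, keep the condition that there is no nominal Safety Follow-up Visit, and replace the Day 687 test with: 'ETT visit 21 days or more after the last dose of study drug (replacing the Safety Follow-up Visit under CSP 9.1.3), on any study day'. State that such visits are excluded from the OL Day 15 to OL Week 96 safety windows. ETT Visits held sooner after the last dose stay in their day windows.

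The cost is one amended note and a small change to the windowing code, using the last-dose date already derived. No new data are needed. The downside is that a few early stoppers lose one by-visit safety value, which moves to the Safety Follow-up row. Values more than 28 days off drug would still be excluded by the TE Period.

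Do not change only the ETT clause of note 5. That would send an early stopper's late ETT Visit to Safety Follow-up while a nominal Safety Follow-up Visit on or before Day 687 still went to a treatment window, creating for efficacy the mismatch described here for safety. Any change there must cover both clauses together. It must also say how late ETT sweat chloride values are handled, because sweat chloride has no Safety Follow-up row in Table 12-1 and is not scheduled at that visit in protocol Table 3-1.
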